2.8.1 Adverse events (AEs)

Week 24 analysis

A treatment-emergent AE for Week 24 is defined as any AE in Epoch 3 that develops after initiation of the study treatments or any event already present that worsens following exposure to the study treatment. Following the definition, AEs occurring after treatment discontinuation will also be considered as treatment-emergent AEs. Treatment emergent AEs will be summarized for Week 24 analysis. The number and percentage of subjects having AEs will be summarized by system organ class, preferred term, and treatment group. Unless otherwise specified, primary system organ will be sorted alphabetically and, within each primary system organ class, the preferred terms will be sorted in descending order of frequency in the investigational study drug arm (LIK066 150 mg qd). If a patient reported more than one AE with the same preferred term, the AE will be counted only once. If a patient reported more than one AE within the same primary system organ class, the patient will be counted only once at the system organ class level. The number and percentage of subjects having AEs will be summarized by system organ class, preferred term, treatment group, and subgroups of interest (glycemic status, age group and sex) as well.

The most frequent AEs ($\geq 2\%$ in any treatment group) will be presented by preferred term in descending order of frequency in the investigational study drug arm, LIK066 150 mg qd.

AEs will also be presented by greatest severity. If a patient reported more than one AE with the same preferred term, the highest severity will be presented. All AEs will be summarized by highest severity, primary system organ class, preferred term, and treatment. If a patient reported

more than one AE within the same primary system organ class, only one AE will be counted for that patient at the highest severity level in the total row for each primary system organ class. Missing severity will be assumed to be severe in the summary table.

AEs suspected to be related to study drug, serious AEs, fatal AEs, and AEs leading to study drug discontinuation, study drug interruption will be summarized by presenting number and percentage of patients with an event by primary system organ class, preferred term, and treatment.

Week 24 on-treatment AEs are defined as any treatment-emergent AEs occurred while patients were on Epoch 3 treatment (captured using treatment start and end date). On-treatment AEs, serious AEs, fatal AEs, AEs leading to study drug discontinuation, and AEs of special interest will also be summarized.

End of study analysis

A treatment-emergent AE for the End of study analysis is defined as any AE that develops after the start of Epoch 4 or any event already present in Epoch 3 that worsens following exposure to the study treatment during Epoch 4. AEs occurring after treatment discontinuation will also be considered as treatment-emergent AEs. The number and percentage of subjects having AEs, SAEs, AEs leading to study medication permanent discontinuation and study drug interruption occurring after start of Epoch 4 will be summarized and presented, in similar way as for the Week 24 analysis.

Overall treatment emergent AEs for the overall 48 weeks of Epoch 3 plus Epoch 4 by 10 randomized treatments will be generated.

All AEs in the database will be listed by 10 randomized arms. The listings will include those AEs reported during the run-in epoch, and AEs reported after study completion or discontinuation.

Legal requirement for AE reporting

For the legal requirements of ClinicalTrials.gov and EudraCT, two required tables on treatment emergent AEs which are not SAEs with an incidence greater than 2% and on treatment emergent SAEs and SAEs suspected to be related to study treatment will be provided by system organ class, preferred term, and 10 randomized treatment arms on the SAF for overall study duration.

If for a same patient, several consecutive AEs (irrespective of study treatment causality, seriousness and severity) occurred with the same SOC and PT:

- a single occurrence will be counted if there is ≤ 1 day gap between the end date of the preceding AE and the start date of the consecutive AE
- more than one occurrence will be counted if there is > 1 day gap between the end date of the preceding AE and the start date of the consecutive AE

For occurrence, the presence of at least one SAE/SAE suspected to be related to study treatment/non SAE has to be checked in a block e.g., among AE's in a ≤ 1 day gap block, if at least one SAE is occurring, then one occurrence is calculated for that SAE.

The number of deaths resulting from SAEs suspected to be related to study treatment and SAEs irrespective of study treatment relationship will be provided by SOC and PT.

2.8.1.1 Adverse events of special interest / grouping of AEs

AEs of special interest, such as risks defined in the development safety profiling plan (DSPP), or topics of interest regarding signal detection or routine analysis, are defined in the electronic case retrieval sheet (eCRS) that is stored in GPS.

The pre-defined issues of special interest for LIK066 including identified risks, potential risks, and special assessments are listed below:

- Bone fractures
- Cardiotoxicity
- Diarrhea
- Electrolyte disturbances
- Genital infections
- Hepatotoxicity
- Hypersensitivity
- Hypoglycemia
- Impaired renal function
- Increased LDL
- Intravascular volume depletion
- Ketoacidosis
- Malignancy
- Pancreatitis
- Urinary tract infections
- Venothrombotic and embolic events
- Lower limb amputation

Week 24 analysis

Treatment-emergent AEs of special interest which occur during Epoch 3 will be summarized by risk category and preferred term, by treatment. The AEs of special interest will be summarized by risk category, preferred term, treatment, and subgroups of interest (glycemic status, age group, and sex) as well.

In addition, exposure-adjusted incidence rates per 100 patient years regardless of study drug relationship, by treatment will be provided by risk category and preferred term. The 95% confidence interval for the overall exposure-adjusted incidence rates per 100 patients will also be presented for each risk category, along with relative risk and 95% confidence interval.

Additional analyses for the pre-defined risks of diarrhea, ketoacidosis and hypoglycemia will be performed as described below:

Diarrhea events of special interest

Number of days with on-treatment diarrhea events will be calculated for all patients with at least one incidence of on-treatment diarrhea and will be summarized descriptively by treatment.

- Number of days for one diarrhea incidence = AE end date – AE start date +1.
- Number of days with diarrhea events for a patient = sum of days on diarrhea over all incidences that occurred in Epoch 3.

The number and percentage of patients with diarrhea events during the double-blind treatment period (while patients on study medication) will also be summarized by treatment over time in the following time window: 0 - <2, 2 - <4, 4 - <8, 8 - <12, 12 - < 16, 16 - < 20 and >= 20 weeks.

The number of days with diarrhea events while on-treatment in Epoch 3 will be analyzed using a generalized linear model assuming a negative binomial distribution. The negative binomial model accounts for any over dispersion that may result from assuming a Poisson distribution by allowing a different Poisson rate for each patient and assuming that these rates as a set are distributed across subjects according to a gamma distribution. The log(overall days on study medication) will be used as the offset variable in the model. The model will be adjusted for treatment, glycemic status, and region.

Ketoacidosis events of special interest

All cases of ketoacidosis will be adjudicated by an independent committee. The frequencies and percentages of the adjudication confirmed ketoacidosis events will be provided by treatment.

The site-reported ketoacidosis events will also be summarized by treatment. In addition, the ketoacidosis events will be listed at individual patient level, with the site-reported event profile and symptoms and the adjudication outcome displayed as well.

Hypoglycemic events of special interest

Hypoglycemic events entered into the study Hypoglycemic event eCRF are included in all of the AE summaries in Section 2.8.1.

In addition, there are two categories clinically significant of hypoglycemic events defined:

- **Severe hypoglycaemia:** An event, requiring assistance of another person (third party assistance) to actively administer carbohydrate, glucagon, or other corrective actions, confirmed or not by a blood glucose measurement
- **Other clinically significant hypoglycaemia:** Plasma glucose < 3.0 mmol/l (54 mg/dl) with or without typical symptoms of hypoglycaemia, and which is handled by the subject himself/herself.

Hypoglycemia classification is included in the Appendix Table 5-1.

Patients reporting at least one clinically significant hypoglycemic event, and the subgroup of patients reporting ≥ 2 such events, patients discontinued study medication or withdrew from the study due to clinically significant hypoglycemic events, patients reporting severe hypoglycemic events, and patients reporting other clinically significant hypoglycemic events will be

summarized by numbers and percentages in each treatment group. The exposure-adjusted incidence rates, relative risks and the related 95% confidence intervals of LIK groups versus placebo for the overall, severe and other clinically significant hypoglycemic incidences will be calculated respectively, and presented along with other safety risks/events of interest.

The clinically significant hypoglycemic events will also be summarized by event profile as follows:

- Severity (Mild, Moderate, Severe)
- Meeting the definition of an SAE (Yes, No)
- Seriousness (Death, Requires or prolongs hospitalization, Life threatening, Congenital anomaly or birth defect, Significant disability, Other medically importance serious event)
- Discontinuation due to hypoglycemic events (Yes, No)
- Relationship to the study treatment (No, Investigational treatment, Other study treatment, Both and/or indistinguishable)
- Action taken with study treatment (Dose increased, Dose not changed, Dose reduced, Drug interrupted, Drug withdrawn, Unknown, Not applicable)
- Medication or therapy taken (Yes, No)
- Outcome (Not recovered/not resolved, Recovered/resolved, Recovered/Resolved with sequelae, Fatal, Unknown)
- Time of the day in 24-hour clock (>00:00–06:00, >06:00–12:00, >12:00–18:00, or >18:00–24:00)
- Time between last meal and event
- Time between last dose and event
- Precipitating factors (None, Missed/delayed meal, Strenuous exercise, Alcohol consumption, Other)
- Third party assistance (Yes, No)
- Medical assistance received (Yes, No)

In addition, for pre-defined risk and selected AEs including hypotension, hypoglycemia, hyperkalemia, diarrhea, genital infections and UTIs, a by-stratification factor of BL glycemic status subgroup analysis will be provided.

A listing of AEs of special interest will be presented by treatment group and patient number.

End of study analysis

The AEs of interest collected during Epoch 4 will be summarized as appropriate separately.

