2.4 Treatments (study treatment, rescue medication, concomitant therapies, compliance)

2.4.1 Study treatment / compliance

Week 24 analysis

The duration of double-blind treatment exposure in Epoch 3 will be summarized by treatment group both descriptively in days (mean, standard deviation, minimum, Q1, median, Q3, and maximum) and by duration category in weeks (≤ 2 , $>2-4$, $>4-8$, $>8-12$, $>12-16$, $>16-20$, $>20-24$, and >24) for the SAF.

- Duration of exposure (days) = last dose date of Epoch 3 – first dose date + 1
- Duration of exposure (weeks) = (last dose date of Epoch 3 – first dose date + 1)/7

Overall subject-years on-treatment in Epoch 3 will be reported by each treatment group.

- Overall subject-years on-treatment = sum of duration of treatment exposure (in days) from all subjects / 365.25

The duration of double-blind treatment exposure excluding treatment interruptions in Epoch 3 will also be summarized descriptively and by duration categories as above.

- Duration of exposure excluding treatment interruptions (days) = last dose date of Epoch 3 – first dose date + 1 – number of days of treatment interruption

Treatment interruptions will be considered as following:

- For BID doses – patients taking 0 tablets for both morning and evening doses,
- For QD doses – patients taking 0 tablets for the morning dose,
- For Placebo – patients taking 0 tablets for both morning and evening doses.

Number and percentage of subjects with treatment interruption and permanent treatment discontinuations in Epoch 3 will be provided by reason for treatment interruption or discontinuation.

Duration of treatment interruption, frequency and duration of the PD after meal dose intake will also be summarized as appropriate.

End of study analysis

The duration of Epoch 4 will be summarized by treatment group both descriptively in days and by duration-category in weeks (≤ 4 , $>4-12$, $>12-24$, and >24) for subjects in the safety set who enter the study Week 24 to Week 48 period (Epoch 4), respectively.

- Epoch 4 duration of exposure (days) = last dose date – first dose date of Epoch 4 + 1
- Epoch 4 duration of exposure (weeks) = (last dose date – first dose date of Epoch 4 + 1)/7

Duration of treatment interruption, frequency and duration of PD after meal dose intake will also be summarized as appropriate.

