5.1.2 AE date imputation

AE date imputation need to be done twice, once for Week 24 analysis, and once for the End of study analysis.

AE end date imputation

1. If ‘month’ is missing, the end date will be set to the earliest of the (min (last visit date, last dose date), 31DECYYYY, and date of death).
2. If ‘day’ is missing, the end date will be set to the earliest of the (min (last visit date, last dose date), 31MONYYYY, and date of death).
3. If ‘year’ is missing or AE is ongoing, the end date will not be imputed.

AE start date imputation

Before imputing AE start date, find the AE start reference date.

- If the (imputed) AE end date is complete and the (imputed) AE end date < treatment start date then AE start reference date = min (informed consent date, earliest visit date).
- Else AE start reference date = treatment start date

After finding the AE start reference date:

1. If ‘year’ is missing, the date uncertainty is too high; therefore the imputed AE start date will be set to NULL.
2. If ‘year’ is less than the treatment start date ‘year’, the AE started before treatment; therefore:
 - a. If ‘month’ is missing, the AE start date will be set to 01JULYYYY.
 - b. If ‘day’ is missing, the AE start date will be set to 15 MONYYYY.
3. If ‘year’ is greater than the treatment start date ‘year’, the AE started after treatment; therefore:
 - a. If ‘month’ is missing, the AE start date will be set to 01JANYYYY.
 - b. IF ‘month’ is not missing, the AE start date will be set to the later of (01MONYYYY, AE start reference date + 1).

4. If 'year' is equal to the treatment start date 'year'
 - a. If 'month' is missing, the AE start date will be set to the AE reference start date +1.
 - b. If 'month' is less than the treatment start 'month', the AE start date will be set to 15MONYYYY.
 - c. If 'month' is equal to or greater than the treatment start 'month', the AE start date will be set to the later of (01MONYYYY, AE start reference date+1).

If complete (imputed) AE end date is available and the imputed AE start date is greater than the (imputed) AE end date, imputed AE start date will be set to the (imputed) AE end date.

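### The diarrhea-days formula gives no duration to an episode recorded as ongoing and does not stop counting at the last Epoch 3 dose, so the count does not match its on-treatment outcome and offset

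*SAP*

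**What the plan says.** SAP 2.8.1.1 sets the length of one episode as "Number of days for one diarrhea incidence = AE end date – AE start date +1". A patient's total is the "sum of days on diarrhea over all incidences that occurred in Epoch 3". The section says this total "will be calculated for all patients with at least one incidence of on-treatment diarrhea and will be summarized descriptively by treatment". It then plans a negative binomial model in which the "number of days with diarrhea events while on-treatment in Epoch 3 will be analyzed", and adds: "The log(overall days on study medication) will be used as the offset variable in the model".

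SAP 5.1.2, which is run separately for the Week 24 analysis, covers end dates. If only the day is missing, the date becomes the earliest of "min (last visit date, last dose date), 31MONYYYY, and date of death". A parallel rule applies when the month is missing. If the year is missing or the "AE is ongoing, the end date will not be imputed".

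SAP 2.4.1 offers two exposure definitions for Epoch 3. One is "Duration of exposure (days) = last dose date of Epoch 3 – first dose date + 1"; the other subtracts days of treatment interruption. SAP 2.8.1.1 does not say which of the two the offset uses.

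**The concern.** The formula needs an end date, and SAP 5.1.2 withholds one from ongoing events. A patient whose only episode is ongoing is promised a count but cannot be given one. No text says whether such an episode scores zero, is dropped, or removes the patient from the model.

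The numerator and the offset also cover different windows. The offset stops when dosing stops, while an episode with a known end date runs to that date. After early discontinuation the extra days are off drug. In a completer they fall in Epoch 4, on a different assigned treatment or on continued placebo. Either way they enter an outcome described as on-treatment in Epoch 3.

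Two programmers following the text could therefore derive different counts from the same records. Protocol 1.1 reports diarrhea as very common in an earlier study at 150 mg qd and gives this as the reason to look for a dose that balances efficacy and tolerability. The day count is the planned output that measures burden rather than occurrence.

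**Working it through.** The documents state no figure for diarrhea days, so there is nothing to reproduce. The check is to read the rules together and then apply them to assumed subjects.

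**Does another section close the gap?**

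- SAP 2.8.1 defines on-treatment AEs by reference to treatment start and end dates. That decides which events qualify, not which of their days count.
- SAP 2.1.1 limits Week 24 data to those collected up to the end of Epoch 3, but its sentence on AEs selects by start date. If it is read as removing later end dates, those episodes become ongoing and lose their duration. It does not reach off-drug days inside Epoch 3 after early discontinuation.
- The cap in SAP 5.1.2 applies to partial end dates only.

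**Worked examples.** These illustrate the rules and do not estimate likely size. Days are study days.

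Formulas: SAP count = end − start + 1. Offset (first-to-last dose, no interruptions assumed) = last dose − first dose + 1. On-treatment count = min(end, last dose) − start + 1. For partial dates, the last visit, the month end and any death are assumed to fall on or after the last dose.

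| Subject | End date record | SAP count | Offset | Count / offset | Days to last dose |
|---|---|---|---|---|---|
| 1. Drug Days 1-14, diarrhea Days 10-17 | complete | 17 − 10 + 1 = 8 | 14 | 0.57 | 14 − 10 + 1 = 5 |
| 1. Same | day missing | 14 − 10 + 1 = 5 | 14 | 0.36 | 5 |
| 1. Same | ongoing | undefined | 14 | – | 5 |
| 2. Drug Days 1-14, diarrhea Days 10-40 (deliberately long tail) | complete | 40 − 10 + 1 = 31 | 14 | 2.21 | 5 |
| 3. Completer, drug Days 1-168, diarrhea Days 150-190 | complete and used | 190 − 150 + 1 = 41 | 168 | 0.24 | 168 − 150 + 1 = 19 |
| 3. Same | read out as after Epoch 3, or still ongoing | undefined | 168 | – | 19 |

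Example 1 shows the inconsistency: a fully known end date gives 8 days and a less well known one gives 5. Example 2 shows that the count can exceed the days on drug. Example 3 shows that one episode can give 41 days or none, when 19 are on Epoch 3 treatment.

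**Direction.** If episodes without a duration contribute nothing, counts fall. Leaving complete end dates uncut raises them. The documents give no episode durations and no share of ongoing episodes, so the net effect cannot be computed.

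**The case against.** Several counter-arguments have force.

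- A reader might infer that every episode spanning Week 24 loses its duration. The documents do not support that. AEs enter by start date, Protocol 7.1 requires follow-up until an event resolves or is judged permanent, and the Week 24 analysis waits for the last subject to finish Epoch 3. Many end dates may be recorded by then. The duration is missing only if the record is still ongoing or the later date is read out under SAP 2.1.1.
- The full length of an episode that began on treatment is a coherent measure of burden, and in the descriptive summary on-treatment qualifies the events. Last dose is also not the SAP's only boundary: SAP 2.5.4 uses last dose plus 7 days for weight, and on that window (14 + 7 = Day 21) all of example 1 would count. This shows that the boundary is a choice. It does not reconcile a whole-episode count with the model's stated outcome and a days-on-medication offset. A ratio above 1 does not break a negative binomial model, but it is not a share of days on drug.
- A reader might infer bias for or against the higher doses, or a threat to dose selection. Neither is supported. The two gaps act in opposite directions, and Protocol 9.4.2 bases target dose selection on model-averaged weight estimates. Protocol 3.3 describes the earlier diarrhea as predominantly mild and declining in frequency in most subjects, which does not suggest that many episodes straddle Week 24.
- SAP 2.1 refers further detail to an appendix of the study report, where a convention might be written. That appendix is not among the documents.

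**Conclusion.** The point stands as a minor one. An explicit formula conflicts with its own stated outcome and offset, and a second rule leaves some qualifying patients without a value. The text of both gaps is clear.

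The effect is confined to the diarrhea-days negative binomial model and the descriptive summary of the same variable. The incidence, exposure-adjusted and time-window summaries do not use the formula, and the primary endpoint is untouched. Size and direction between arms are unknown. The examples rest on assumed dates, uninterrupted dosing and the first-to-last-dose reading of the offset.

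**What to change.** In SAP 2.8.1.1, for both outputs:

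1. Count days from the later of AE start and first Epoch 3 dose to the earlier of AE end and last Epoch 3 dose.
2. Censor episodes recorded as ongoing at the last Epoch 3 dose.
3. State which exposure definition in SAP 2.4.1 the offset uses (first-to-last dose, or excluding interruptions), and treat interruption days the same way in the count and the offset.
4. State one main-analysis rule for resolved episodes with a wholly unknown end date, report how many there are, and vary the rule in a sensitivity analysis. The choice matters: extending such an episode to the last dose would give a completer with onset on Day 10 a count of 168 − 10 + 1 = 159 days.

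The cost is a few sentences, one derived variable and two outputs, with no new data. The SAP history entry of 11 May 2018 already refers to Week 24 results. If these outputs exist, document the handling that was used and rerun both as a labelled sensitivity analysis.

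### The diarrhea-days rule in SAP 2.8.1.1 sums event lengths, so a calendar day shared by two diarrhea records is counted twice in the negative binomial outcome

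*SAP*

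**What the plan says.** The derivation is in SAP 2.8.1.1, under diarrhea events of special interest. The length of one event includes both end dates: "Number of days for one diarrhea incidence = AE end date – AE start date +1". The patient's total is a plain sum: "Number of days with diarrhea events for a patient = sum of days on diarrhea over all incidences that occurred in Epoch 3". The SAP does not define an incidence and has no rule that a date covered by two records counts once.

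The total is used twice. It is summarized by treatment among patients with at least one on-treatment event, and it is modeled: "The number of days with diarrhea events while on-treatment in Epoch 3 will be analyzed using a generalized linear model assuming a negative binomial distribution". Exposure enters through the offset: "The log(overall days on study medication) will be used as the offset variable in the model".

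The only rule in the SAP that joins AE records is in 2.8.1, under the registry requirements: "For the legal requirements of ClinicalTrials.gov and EudraCT, two required tables on treatment emergent AEs which are not SAEs". It applies to consecutive AEs of one patient with identical system organ class and preferred term, and reads: "a single occurrence will be counted if there is ≤ 1 day gap". The gap runs from one record's end to the next one's start. The diarrhea section does not refer to this rule.

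On coding, SAP 2.8.1.1 says: "Treatment-emergent AEs of special interest which occur during Epoch 3 will be summarized by risk category and preferred term, by treatment". The terms that make up the diarrhea category are held in an electronic case retrieval sheet, which is not among the documents.

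**The concern.** The variable is named as a number of days, but the rule adds durations. The two agree only when no two diarrhea records of a patient share a date. The SAP foresees that one event may be recorded as several AEs, because its registry rule joins consecutive records of the same term whatever their severity. Nothing comparable protects the day count.

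This total is the outcome of the only model planned for the duration of diarrhea. Protocol 1.1 names diarrhea as the reason to look for a dose that balances efficacy and tolerability, and Protocol 3.3 gives tolerability as one reason to test twice-daily dosing. Diarrhea days by arm bear on that comparison. An outcome that can be larger than the exposure it is divided by is also not a proper rate of days with diarrhea per day on drug.

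**Working it through.** The documents state no expected number of diarrhea days, so there is no planned figure to reproduce. The check applies the SAP rule to assumed dates and compares it with the number of distinct calendar days covered.

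**Inputs.** Length of one incidence = end − start + 1, and patient total = sum over incidences (both SAP 2.8.1.1). One incidence is read as one AE record, because the formula uses one AE start date and one AE end date. The dates below are assumptions.

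**Step 1: the rule against distinct days.**

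| Assumed records (study days) | SAP sum | Distinct days | Excess |
|---|---|---|---|
| 10–14 and 15–19 (next day) | 5 + 5 = 10 | 10 | 0 |
| 10–14 and 14–19 (shared boundary) | 5 + 6 = 11 | 10 | 1 |
| 10–13, 13–16 and 16–19 | 4 + 4 + 4 = 12 | 10 | 2 |
| 10–16 and 14–19 (partial overlap) | 7 + 6 = 13 | 10 | 3 |
| 10–19 twice (two preferred terms, same dates) | 10 + 10 = 20 | 10 | 10 |
| 10–14 and 20–24 (two preferred terms, separate dates) | 5 + 5 = 10 | 10 | 0 |

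The excess equals the number of extra times that shared dates are counted. A split into records, or a difference in coding, adds nothing by itself.

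**Step 2: against the offset.** Epoch 3 lasts 24 weeks, or 24 × 7 = 168 days. Two records that each cover all 168 days give 168 + 168 = 336 diarrhea days against 168 days on drug. This is an extreme case, but it shows that the rule sets no ceiling.

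**Step 3: effect on means and rate ratios.** Let q be the share of an arm's true diarrhea days that are covered by a second record. The SAP sum is then true days × (1+q). The documents give no value of q. For q from 5% to 30%, mean days are multiplied by 1.05 to 1.30. With qA in the active arm and qP on placebo, the rate ratio is multiplied by (1+qA)/(1+qP):

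- 10% and 10%: 1.10/1.10 = 1.00
- 10% and 0%: 1.10/1.00 = 1.10
- 20% and 5%: 1.20/1.05 = 1.14
- 30% and 5%: 1.30/1.05 = 1.24

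**Step 4: would the registry rule repair it?** Joining records with a gap of at most one day would return 10 for the shared-boundary row. But the rule is written for the registry tables, counts occurrences rather than days, and requires the same preferred term. It therefore leaves concurrent terms unjoined even if it were borrowed.

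**The case against.** The strongest reply is that the harm is not demonstrated. Protocol 7.1 has an AE followed to resolution with severity reassessed at each visit, and no text says that a change in severity opens a new record. Whether the diarrhea category holds several preferred terms cannot be seen. The registry rule covers consecutive records, including next-day ones that the sum handles correctly, so it is no evidence that overlaps occur in this trial. All of that stands, and it limits what can be said about size.

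It also rules out two stronger readings. A reader might infer that every adjacent or differently coded pair of records is double counted; the first and last rows of the table show that this is not so. A reader might also infer that the rule inflates the high-dose ratio against placebo, on the thought that longer diarrhea produces more records. The documents contain nothing on overlap by arm, and with equal q the ratio is unchanged.

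It is also fair to say that this is one safety analysis among several. The percentages of patients by time window and the exposure-adjusted incidence rates do not use the day count. The negative binomial model does allow for extra variance, but that does not correct a mean that has been counted too high.

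What the reply does not remove is the rule itself. It is explicit, and followed literally it gives a wrong count whenever two records share a date.

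**Conclusion.** The point holds in a limited form. SAP 2.8.1.1 counts a shared boundary date once too often and counts overlapping days twice, including days with concurrent preferred terms in the diarrhea category. Descriptive day counts are overstated wherever this happens. The rate ratio is distorted only if the share of doubly covered days differs between arms: by 1.10 for 10% against 0% and by 1.14 for 20% against 5%. These are illustrations under assumed shares, not estimates. They assume that no day is covered by more than two records and that the overlap scales the arm's mean by a constant factor. Neither the frequency nor the direction can be determined from the documents.

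The conclusion rests on reading one incidence as one AE record, which is natural but not stated; the missing definition is part of the problem. The primary dose-response test, its alpha and the power are unaffected.

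**What to change.** Replace the two formulas in SAP 2.8.1.1 with one definition: the number of distinct calendar days, from first to last Epoch 3 dose, covered by at least one AE in the diarrhea risk category. Records are cut off at the last dose.

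The cut-off is needed. With dosing on Days 1–20 and diarrhea on Days 5–40, distinct days alone give 40 − 5 + 1 = 36 against 20 days on drug. With the cut-off, the count is 20 − 5 + 1 = 16 and cannot exceed the offset. For this to hold, the offset must be the same first-to-last-dose span. SAP 2.4.1 also defines an exposure net of interruptions, so the text should say which one is meant. It should also say how an ongoing event is closed, because SAP 5.1.2 leaves its end date unimputed; running it to the last Epoch 3 dose would fit this definition.

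The cost is one or two sentences and a small programming change. Where no records share dates and none runs past the last dose, the counts do not change. The SAP's document history already refers to Week 24 results in May 2018. If the Week 24 model has been run, the corrected count should be a documented re-analysis shown beside the result already obtained.
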